1.0 PROTOCOL SUMMARY AND/OR SCHEMA

This is a double-blinded, randomized trial comparing adjuvant treatment with the WT-1 analog peptide vaccine plus Montanide adjuvant + GM-CSF to treatment with Montanide + GM-CSF in patients with malignant pleural mesothelioma (MPM) who have completed combined modality therapy. Thirty-nine patients will be enrolled in each arm. The primary endpoint is the 1-year progression-free survival rate in each of the two arms.

- **Malig Pleural Meso**
- **WT-1 positive**
- **4-12 weeks since completion of multi-modality treatment including surgery**
- **PS \geq 70%**

R
A
N
D
O
M
I
Z
E

Specific Immunotherapy:
WT-1 vaccine / Montanide + GM-CSF

Non-specific Immunotherapy:
Montanide + GM-CSF

Primary endpoint: 1-year PFS

Aim to increase from 50% to 70%

N=78 patients (39 per arm)

As specified in the statistical section in the protocol, an interim analysis took place to assess for futility. At the time of this analysis ≥ 10 out of the first 20 patients had experienced progression within 1 year. As a result of these findings, enrollment to the control arm (GM-CSF + Montanide) was recommended to be closed, while enrollment to the study arm continues pending further follow up data. This amendment (6/2015) addresses this change in trial design.

2.0 OBJECTIVES AND SCIENTIFIC AIMS

Primary Objective: To assess the 1-year progression free survival in patients treated with WT-1 analog peptide vaccine + GM-CSF or Montanide + GM-CSF after completion of combined modality therapy for MPM.

Secondary Objectives:

- 1) To confirm the immunogenicity of the WT-1 analog peptide vaccine in patients with MPM after completion of combined modality therapy.
- 2) To assess the utility of using the serum marker, soluble mesothelin related protein (SMRP), in monitoring patients with MPM for disease progression.

Amended: 7/14/15

MEMORIAL SLOAN-KETTERING CANCER CENTER IRB PROTOCOL

IRB#: 10-134 A(8)

- 3) To assess the overall survival of patients treated with WT-1 analog peptide vaccine + GM-CSF or Montanide + GM-CSF after completion of combined modality therapy for MPM.

3.0 BACKGROUND AND RATIONALE

Malignant Pleural Mesothelioma (MPM) – There are between 2000 and 3000 new cases of MPM diagnosed annually in the United States. Its epidemiology has been linked to asbestos with a latency period of 25 years or more between exposure and disease onset, though only about two-thirds of patients report a clear history of asbestos exposure. MPM is notoriously difficult to treat. Only one chemotherapy regimen has been FDA approved for the treatment of mesothelioma (pemetrexed and cisplatin). This approval was based on the results of a phase III trial demonstrating that treatment with the combination of pemetrexed and cisplatin improved survival over treatment with cisplatin alone, but the benefit was small. The overall median survival improved from 9.3 months to 12.1 months ($p=0.20$) and the 1-year survival improved from 38% to 50%.¹

For patients with early stage mesothelioma, surgical resection by pleurectomy/decortication or extrapleural pneumonectomy may be considered. Since the tumor essentially encases the entire lung and often invades the chest wall or mediastinum, even radical surgical resection typically leaves disease behind. For that reason, multimodality therapy is usually advised, adding radiation and chemotherapy to the treatment plan. In retrospective data series, multimodality therapy offers higher survival rates than surgery alone.² Treating the pleura with radiation offers a major challenge in delivering adequate doses without damaging the underlying lung. However, hemithoracic radiation after extrapleural pneumonectomy is safe and decreases the risk of local control.³ Chemotherapy is used in an effort to decrease systemic relapse. In a multicenter study led by our institution, 77 patients received induction pemetrexed/cisplatin, and if no progression, extrapleural pneumonectomy, and hemithoracic radiation.⁴ The overall median survival was only 17 months. For the 40 patients who completed all therapy, the median survival was a more promising 30 months. Nearly all patients recurred. Additional, less toxic therapies that could control residual disease after this aggressive treatment program are needed.

Wilms' tumor 1 (WT-1) – The Wilms' tumor suppressor gene, WT1, was first identified in childhood renal tumors, but WT1 is also highly expressed in multiple other hematologic malignancies and solid tumors, and, in particular, mesothelioma^{5 6}. WT1 was originally identified by cDNA mapping to a region of chromosome 11p13. The WT1 cDNA encodes a protein containing four Kruppel zinc fingers and contains a complex pattern of alternative splicing resulting in four different transcription factors. Each WT1 isoform has different DNA binding and transcriptional activities⁷, and can positively or negatively regulate various genes involved in cellular proliferation, differentiation, apoptosis, organ development and sex determination. WT1 is normally expressed in tissues of the mesodermal origin during embryogenesis including the kidney, gonads, heart, mesothelium and spleen⁸. In normal adult tissues, WT1 expression is limited to low levels in the nuclei of normal CD34+ hematopoietic stem cells, myoepithelial progenitor cells, renal podocytes and some cells in the testis and ovary⁹. WT1 is highly homologous in mice and humans (96% at the amino acid level) and has similar tissue distribution and function^{10,11}. Although originally described as a tumor suppressor gene, the WT1 proteins appear to be involved in tumorigenesis.

MEMORIAL SLOAN-KETTERING CANCER CENTER IRB PROTOCOL

IRB#: 10-134 A(8)

The strong expression of WT-1 protein in mesothelioma makes it a rationale target for therapeutics. The expression is so high, that pathologists routinely use immunohistochemical stains for WT-1 to help distinguish epithelial mesothelioma from pulmonary adenocarcinoma. In three different pathology series, the rate of WT-1 nuclear staining ranged from 72% to 93%.¹²⁻¹⁴

Development of a WT-1 peptide vaccine: Although WT-1 is a nuclear protein, it is processed and presented on the cell surface. For this reason, WT-1 is an attractive target for immunotherapy⁵. WT1 protein is a self-antigen, and, as a result, breaking tolerance is a potential problem for effective vaccination. One strategy to circumvent the poor immunogenicity of tumor-associated peptides at the surface of target cells is to design synthetic analogue peptides that will be more immunogenic. Such peptide analogues could generate an immune response that not only recognizes the immunizing epitopes, but also cross-reacts with the original native peptides; this is known as a heteroclitic response. By using computer prediction analysis, we designed a large number of synthetic peptides derived from WT-1 protein sequences in which single or double amino acid substitutions were introduced into the peptides at key HLA A0201 binding positions. Peptides predicted to bind with high affinity to HLA A0201 molecules were directly assayed for their ability to stabilize MHC class I A0201 molecules on the surface of TAP negative T2 cell line. The new peptides could stabilize MHC class I A0201 molecules better than native sequences. Avidly binding peptides were then assayed in an antigen specific T-cell expansion in vitro system for ability to elicit HLA restricted, peptide specific CTL responses using purified T cells from healthy donors. Two synthetic analogue peptides generated more effective immune responses than the native peptides. In addition, CD8+ T cells stimulated with the new synthetic peptides displayed heteroclitic features and cross-reacted with the native WT-1 peptides and also were able to mediate peptide specific cytotoxicity. Importantly, T cells stimulated with the new synthetic peptides cross-reacted with the native WT1 peptide sequence and were able to kill HLA matched CML blasts.¹⁵

Peptides capable of stimulating CD4+ response are necessary for inducing T-cell memory. WT1 analog peptides are capable of stimulating a peptide-specific CD4+ response that can recognize WT1+ tumor cells in multiple HLA-DRB1 settings. Using cross priming experiments, it was shown that WT1 peptide is presented on the surface of mesothelioma tumor cells and could be recognized by the T cells stimulated by the individual WT1DR peptides. Human T cells stimulated with the analog WT1A1 can kill WT1+ mesothelioma cell lines.¹⁶

In conclusion, analog heteroclitic WT1 peptides with increased immunogenicity can be synthesized and are potential vaccine candidates. To these peptides we have added 2 longer WT1 sequences that are capable of inducing CD4 responses in vitro. The 4 peptides with an immunological adjuvant constitute our vaccine.

The vaccine includes 3 peptides designed to stimulate common HLA-DR expressing cells in addition to 1 peptide for HLA-A0201 cells. Therefore, the relevant HLA alleles include HLA-DR B- 1, 4, 7, 11, and 15 (and possibly others), which together with A0201 should cover most patients. Assuming the peptides are immunogenic to one of these HLA types, immunologic responses should be seen in a large fraction of the cohort.

MEMORIAL SLOAN-KETTERING CANCER CENTER IRB PROTOCOL

IRB#: 10-134 A(8)

Immune Adjuvants: Montanide ISA 51 VG is an immune adjuvant that contains a natural metabolizable oil and a refined emulsifier similar to mannide monooleate. We have selected Montanide ISA 51 VG due to its established efficacy as an adjuvant and its lack of toxicity. It has proven safe and relatively nontoxic at the dose level proposed and highly effective at augmenting immunogenicity in several clinical trials of cancer vaccines ^{17,18}. Several melanoma vaccines containing various protein antigens plus Montanide induce cytotoxic T cells against target cells expressing these antigens, and some clinical responses were seen ¹⁷⁻¹⁹. Side effects have been mild, and mainly characterized by grade 1-2 discomfort at the injection sites.

Recombinant Sargramostim (GM-CSF) is a human protein grown in a yeast (*S. cerevisiae*) vector. Sargramostim (GM-CSF) promotes clonal expansion and differentiation of hematopoietic progenitor cells, antigen presenting cells, and dendritic cells. Partially committed progenitor cells divide and differentiate in the granulocyte/macrophage pathway. In addition to having extensive clinical application in promoting granulocyte recovery after cytotoxic chemotherapy, Sargramostim (GM-CSF) has been found to promote activation of T cells and dendritic cells making it an attractive immune adjuvant. It has been used in conjunction with other adjuvants or alone in several clinical vaccine trials which demonstrated immune as well as clinical responses ^{17,18,20-22}.

Pilot Trial with WT-1 Vaccine in Patients with Thoracic and Hematologic Malignancies: At MSKCC, we conducted a pilot trial to determine the immunogenicity and safety of vaccination with our WT1 heteroclitic peptides in humans (IRB 06-085).²³ As described above, in order to broaden the immune response in the setting of varied HLA subtypes, four different peptides were included in the vaccine. Peptides were suspended in Montanide adjuvant, and GM-CSF was administered at the injection site.

In one arm of the study, we enrolled primarily patients with mesothelioma. These patients had unresectable or relapsed disease and had received no more than one prior pemetrexed containing chemotherapy regimen. Patients with NSCLC, either stage III or IV after completion of initial treatment with surgery and/or chemotherapy and/or radiation therapy, were also eligible. Patients were required to have tumors that showed immunohistochemical staining for WT1 in greater than 10% of cells. At least 4 weeks must have elapsed between the patient's last chemotherapy or radiation treatment and the first vaccination. All HLA subtypes were eligible, though the HLA subtype was determined for the purposes of measuring immune response.

Therapy consisted of six vaccinations of the WT1 peptide (200 mcg per peptide, 800 mcg total combined with Montanide to a total volume of 1.0 mL) administered weeks 0, 4, 6, 8, 10, and 12. All vaccinations were administered subcutaneously with vaccination sites rotating between extremities. Injection sites were pre-stimulated with Sargramostim (GM-CSF) (70mcg) injected subcutaneously on days -2 and 0. Patients who had a clinical, molecular, or immunologic response and did not have disease progression were able to continue with up to 6 more vaccinations administered approximately every month. Immune responses were measured by T-cell proliferative response and delayed type hypersensitivity (DTH) against WT-1 peptides. In patients with adequate samples, T-cell gamma interferon release as measured by ELISPOT was performed as well.

MEMORIAL SLOAN-KETTERING CANCER CENTER IRB PROTOCOL

IRB#: 10-134 A(8)

Oka and colleagues in Japan conducted a Phase I clinical study of immunotherapy targeting the WT1 protein in patients with leukemia, MDS, lung cancer, or breast cancer.¹⁹ Patients were intradermally injected with an HLA-A*2402-restricted, natural, or modified 9-mer WT1 peptide emulsified with Montanide ISA51 VG UFCH adjuvant at 0.3, 1.0, or 3.0 mg per body at 2-week intervals, with toxicity and clinical and immunological responses as the principal endpoints. Twenty-six patients received one or more WT1 vaccinations, and 18 of the 26 patients completed WT1 vaccination protocol with three or more injections of WT1 peptides. Toxicity consisted only of local erythema at the WT1 vaccine injection sites in patients with breast or lung cancer or acute myeloid leukemia with adequate normal hematopoiesis. Severe leukocytopenia occurred in patients with myelodysplastic syndrome with abnormal hematopoiesis derived from WT1-expressing, transformed hematopoietic stem cells. Twelve of the 20 patients for whom the efficacy of WT1 vaccination could be assessed showed clinical responses such as reduction in leukemic blast cells or tumor sizes and/or tumor markers. A clear correlation was observed between an increase in the frequencies of WT1-specific cytotoxic T lymphocytes after WT1 vaccination and clinical responses. It was therefore demonstrated that WT1 vaccination could induce WT1-specific cytotoxic T lymphocytes and result in cancer regression without damage to normal tissues in the clinical setting.

Letsch and colleagues in Germany reported the preliminary findings from their study vaccinating 14 patients with AML or MDS with an HLA-A2 restricted WT1 peptide with KLH and GM-GSF adjuvants. Interestingly, they detected IgM and IgG responses to WT-1 in about 15% of patients before treatment. The vaccine augmented IgM responses in 6 of 6 patients at week 26 or 30, though no CD4 T-cell or IgG responses were noted.

MEMORIAL SLOAN-KETTERING CANCER CENTER IRB PROTOCOL

IRB#: 10-134 A(8)

A search of www.clinicaltrials.gov identifies ongoing studies of WT-1 immune-directed therapy that are being conducted by Duke University, Glaxo-Smith Kline, and the NIH.

GM-CSF: GM-CSF has been used in a number of vaccines studies as an immunologic adjuvant with the presumed benefit mediated through effects on dendritic and other antigen-presenting cells. Several human vaccine studies in melanoma and other human malignancies have reported both encouraging immunologic and clinical results. More recently, two melanoma vaccine studies have reported a deleterious effect of GM-CSF when used as a vaccine adjuvant.^{25,26} While it is important to be cognizant of such a potential negative effect, this study uses a different vaccine with a different dose of GM-CSF in a different disease. Other peptide vaccines studies have used GM-CSF as an adjuvant without negative results.^{27,28}

Rationale for study design: We have chosen to test the efficacy of our WT-1 peptide vaccine in MPM patients who have minimal disease burden after completion of multimodality therapy, but remain at exceedingly high risk for recurrence. Designing a clinical trial to show a benefit from a cancer vaccine is notoriously challenging. Single arm studies showing prolonged time to progression or survival are fraught with patient selection bias. The only way to avoid this bias and show that a vaccine has provided a benefit is by conducting a randomized trial. In this case, we chose to study treatment with Montanide and GM-CSF in one arm. Some immunologists would argue that the use of immune stimulants, such as GM-CSF, could provide a non-specific immune response resulting in some anti-tumor effects. Indeed, this has been observed in studies in prostate cancer and melanoma^{29,30}. The other arm will receive treatment with GM-CSF plus more targeted immunotherapy with WT-1 vax/Montanide. Although the size of this randomized phase II trial precludes direct comparison of the two arms, it will provide valuable information regarding the utility of immunotherapy in the adjuvant setting for this disease. If this study yields promising results, a larger randomized phase III trial would be warranted for confirmation of benefit from WT-1 vax.

Serum markers: In this study, patients will receive the WT-1 vaccine at the time of minimal residual disease after completion of multimodality therapy. We are using standard imaging studies (ie CT scans) to document the time of recurrence. However, imaging of MPM is notoriously challenging due to the pattern of spread along the pleura or the peritoneum. This could be particularly true in this setting due to post-operative changes or radiation effects. Thus, this study provides an optimal clinical scenario to assess the utility of novel serum markers which have the potential to be more sensitive for monitoring disease status.

Mesothelin, a cell surface protein, is shed into the serum of patients with mesothelioma and is a promising tumor marker. It can be measured using a commercially available test kit as soluble mesothelin-related peptide (SMRP).³¹ Elevated SMRP levels can also occur in metastatic adenocarcinomas, especially ovarian and pancreatic. SMRP levels may reflect tumor load and disease progression. The role of SMRP in predicting mesothelioma development in subjects exposed to asbestos has raised significant interest in using SMRP as a tumor marker.³²

4.0 OVERVIEW OF STUDY DESIGN/INTERVENTION

Amended: 7/14/15

Page 14 of 30

MEMORIAL SLOAN-KETTERING CANCER CENTER IRB PROTOCOL

IRB#: 10-134 A(8)

4.1 Design

The study will be a randomized phase II trial to determine the 1-year progression free survival after treatment with WT-1 analog peptide vaccine in patients with MPM after completion of combined modality therapy. Seventy-eight will be enrolled (39 in each arm). One group will receive a preparation of WT-1-derived native and synthetic peptides plus immunologic adjuvant Montanide ISA 51 VG (Seppic Pharmaceuticals, Fairfield, NJ.) and Sargramostim (GM-CSF). The other group will receive Montanide adjuvant + GM-CSF.

4.2 Intervention

Patients will receive 6 injections over 12 weeks. Routine toxicity assessments will continue throughout the trial. Immune responses will be evaluated at baseline and at week 12 by CD4 T cell proliferation, CD4 and CD8 T-cell interferon release. If patient is removed from study prior to week 12 they will have their immunologic blood work checked at the time of study removal. A CT scan of the chest will be performed at baseline, week 12 and then every 3 months thereafter for up to two years until disease progression. The serum tumor marker, SMRP, will be obtained at baseline, at weeks 6 and 12 and then every 3 months thereafter for up to two years until disease progression.

5.0 THERAPEUTIC/DIAGNOSTIC AGENTS

5.1 WT-1 Vaccine: The vaccine contains four separate WT1 peptides:

- WT1-A1: HLA class I peptide with a mutated amino acid R126Y to stimulate CD8⁺ responses.
- WT1-122A1 long: HLA class II peptide containing an embedded WT1-A1 heteroclitic sequence within the longer peptide to stimulate both CD4⁺ and CD8⁺ responses according to data from preclinical and phase 1 studies.
- WT1-427 long and WT1-331 long: HLA class II peptides inducing CD4⁺ responses that could provide help for long lasting CD8⁺ T cell responses.

Name: WT-1 Vax

Structural Formula: The amino acid sequences are:

Name of Peptide	Sequence
WT1-A1	YMFPNAPYL
WT1-122A1long	SGQAYMFPNAPYLPSCLES
WT1-427long	RSDELVRHHNMHQQRNMTKL
WT1-331long	PGCNKRYFKLSHLQMHSRKHTG

Drug Product: WT-1 Vax was manufactured at AmbioPharm, Inc. The four peptides are provided in a sterile solution with phosphate buffered saline to produce the vaccine product. Each vial contains 280 µg of each peptide in a total volume of 0.7 ml (0.4 mg/ml of each peptide, overfill of 40%). Vialing under GMP conditions and sterility testing was performed by University of Iowa Pharmaceuticals. It will be shipped directly to individual sites at -70 to -90° C. The vaccine emulsion will be individually prepared prior to use. This will require mixture of the peptide solution with the immunologic adjuvant Montanide ISA 51 VG.

MEMORIAL SLOAN-KETTERING CANCER CENTER IRB PROTOCOL

IRB#: 10-134 A(8)

Formulation: WT-1 Vax is emulsified with Montanide ISA 51 VG by pharmacists in response to a physician order to treat a protocol patient. The peptide vaccine product and Montanide ISA 51 VG are provided in separate vials. The vaccine product containing 4 WT1 peptides (280 µg each, total 1120 µg) is mixed at a 1:1 (v:v) ratio with Montanide ISA 51 VG as an emulsion in Phosphate buffered saline to a total volume of 1.4 ml. The peptide and Montanide mixture is then vortexed in a Fisher Scientific vortex machine running at highest speed (>3000rpm) for 12 minutes with the use of an attachment. This preparation will take place in the Investigational Pharmacy. The emulsified solution should be administered to the patient within 2 hours of preparation. The dose, 1ml of the emulsion containing 200 µg of each peptide, will be drawn up into a 1-3 ml syringe using an 18 gauge needle. The dose will then be injected into the patient subcutaneously using a 25 gauge needle.

Dose: The 200 mcg dose for each peptide was chosen because it is within the range of safe and active doses used by others. Peptide vaccines have generated immune and clinical responses within a wide range of doses (100-2000 mcg injected) without clear evidence of dose- response relationships. Higher doses have the theoretical possibility of stimulating lower affinity TCRs on T cells and making a reduced response. [1]

Route: Subcutaneous

Storage: Vials of WT1 Vax should be stored at or below -70° C until use.

IND: This vaccine will be administered under an IND held by Memorial Sloan Kettering Cancer Center. MD Anderson will separately apply for an IND to administer the identical vaccine at their center using an identical protocol. Data will be combined for analysis.

5.2 Montanide ISA 51 VG: An water-in-oil (w/o) emulsion with immunoadjuvant activity. Montanide ISA 51 VG appears to act by enhancing the immune system's cytotoxic T-lymphocyte (CTL) response against antigen(s) in vaccines. The surfactant mannide monooleate in Montanide ISA 51 VG contains vegetable-grade (VG) oleic acid derived from olive oil. The adjuvant is stored between 4°C and 40°C, preferably 15°-20°C. Current shelf life in ampule is 5 years. See above for instructions on its use in this study.

5.3 Sargramostim (GM-CSF): Please refer to the package insert in Appendix 4. Sargramostim (GM-CSF) will be administered at a dose 70 mcg (0.14mL) as a subcutaneous injection at the site of vaccination on day -2 and day 0. Sargramostim (GM-CSF) is available in both a lyophilized and a liquid form and is manufactured by Bayer Healthcare Pharmaceuticals. Lyophilized Sargramostim is a sterile white, preservative free powder (250 mcg) that requires reconstitution with 1 mL sterile water for injection, USP or 1 mL bacteriostatic water for injection, USP. Liquid Sargramostim is formulated as a sterile, preserved (1.1% benzyl alcohol), injectable solution (500mcg/ml) in a vial. The liquid may be stored for up to 20 days at 2-8° degrees C once the vial has been entered. After 20 days the remaining solution in the vial should be discarded. Refer to the "Preparation of Leukine" section in the package insert in Appendix 4 for storage of lyophilized Sargramostim following reconstitution with either sterile water for injection, USP or bacteriostatic water for injection, USP. If required, other prescribing information for Sargramostim (GM-CSF) can be found on the MSKCC formulary intranet website.

MEMORIAL SLOAN-KETTERING CANCER CENTER IRB PROTOCOL

IRB#: 10-134 A(8)

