9.0 TREATMENT/INTERVENTION PLAN

- Patients will be treated as outpatients.
- Treatment will be administered on weeks 0, 2, 4, 6, 8, and 10.
- All injections will be administered subcutaneously with sites rotated among extremities.
- Patients will be randomized to receive either non-specific immune therapy (Montanide adjuvant + GM-CSF) or GM-CSF plus the WT-1 peptide vaccine with Montanide adjuvant:

All patients will receive Sargramostim (GM-CSF) (70 mcg) injected subcutaneously on days 0 and -2 of each vaccination. Patients may self administer the Sargramostim (GM-CSF) on day -2 if they have been appropriately instructed on SQ injection administration. Patients will be informed of the expected reactions such as irritation at the injection site. Patients will keep a logbook noting the time and placement of the injection.

Patients will also receive 1.0 ml of emulsion with Montanide alone or with WT-1 peptides plus Montanide. It will be administered by a nurse (it may not be self-administered) subcutaneously to the same anatomical site as

MEMORIAL SLOAN-KETTERING CANCER CENTER IRB PROTOCOL

IRB#: 10-134 A(8)

the GM-CSF. This site will be marked by the patient or treating healthcare professional by a permanent marker pen.

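### Does the single 0.14 mL volume for the 70 mcg GM-CSF dose conflict with the two product strengths described in Section 5.3?

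*Combined protocol and SAP*

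**What the plan says.** Section 5.3 of the combined protocol and SAP gives the GM-CSF dose as a mass followed by a bracketed volume: the drug "will be administered at a dose 70 mcg (0.14mL) as a subcutaneous injection at the site of vaccination on day -2 and day 0". It next notes that "Sargramostim (GM-CSF) is available in both a lyophilized and a liquid form". The lyophilized form is a "preservative free powder (250 mcg) that requires reconstitution with 1 mL sterile water for injection" (bacteriostatic water is the alternative diluent), and the liquid is an "injectable solution (500mcg/ml) in a vial". The reader is sent to a "section in the package insert in Appendix 4 for storage of lyophilized Sargramostim following reconstitution". Section 5.3 does not say which form 0.14 mL refers to.

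Elsewhere the dose appears by mass only:

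- Section 3.0, on the pilot trial: "Injection sites were pre-stimulated with Sargramostim (GM-CSF) (70mcg) injected subcutaneously on days -2 and 0".
- Section 9.0, the treatment plan: "All patients will receive Sargramostim (GM-CSF) (70 mcg) injected subcutaneously on days 0 and -2 of each vaccination". It gives neither a volume nor a form. The same section lets an instructed patient self-inject on day -2.
- Section 11.0: a total of 140 micrograms per vaccination cycle.

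Section 20.0 lists a site-specific addendum (Appendix 2), the package insert (Appendix 4) and a GM-CSF administration log (Appendix 6). Their contents are not in the text available for review.

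**The concern.** A volume corresponds to a mass only at a stated concentration. Section 5.3 gives one volume and then describes two products whose strengths differ by a factor of two. The handling text for the powder (diluents, and storage after reconstitution) suggests that it might be used. If it were, and someone drew up 0.14 mL because that is the figure printed beside the dose, the patient would receive half the stated mass.

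GM-CSF is specified for every patient in both arms, and some day -2 injections may be given at home. Any such slip would lower the delivered adjuvant dose without the protocol text exposing it. The total of 140 micrograms per cycle in Section 11.0 would then not describe what was given.

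**Working it through.** **Inputs**

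- Dose per injection: 70 mcg (Sections 5.3 and 9.0).
- Bracketed volume: 0.14 mL (Section 5.3).
- Liquid strength: 500 mcg/mL (Section 5.3).
- Powder: 250 mcg in 1 mL of diluent (Section 5.3), so nominally 250 / 1 = 250 mcg/mL. This strength is derived, not stated. It ignores the volume of the powder itself, which could only make the solution weaker.
- Injections per vaccination: two, on day -2 and day 0 (Sections 5.3 and 9.0).

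**Step 1: reproduce the plan's figure.** Volume = dose / concentration. For the liquid, 70 / 500 = 0.14 mL, which is the stated volume exactly. In reverse, dose / volume = 70 / 0.14 = 500 mcg/mL. The pair therefore identifies its own concentration, which is that of the liquid.

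**Step 2: apply the same volume to each form.** Mass = volume × concentration.

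| Form | Strength (mcg/mL) | Mass in 0.14 mL | Two injections per cycle |
|---|---|---|---|
| Liquid | 500 | 0.14 × 500 = 70 mcg | 2 × 70 = 140 mcg |
| Reconstituted powder (nominal) | 250 | 0.14 × 250 = 35 mcg | 2 × 35 = 70 mcg |

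The liquid row reproduces the 140 micrograms in Section 11.0. The powder row shows what would follow if the volume were carried over to that form.

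**Step 3: compare the mass dose across sections.** Section 3.0 (pilot), Section 5.3 and Section 9.0 each give 70 mcg per injection. Section 11.0 gives 140 mcg per cycle, which is 2 × 70. No two sections disagree on mass.

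**Step 4: ask what it takes to reach 35 mcg.** Three things must all happen: the powder is dispensed; the bracketed volume is followed although the mass stands immediately before it; and neither the package insert, the log nor staff correct it. No available passage says that any of these occurred. Section 9.0 requires self-injecting patients to be appropriately instructed, and it does not say that they reconstitute powder or work out a volume.

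**Step 5: trace the effect on inference.** Under Section 14.0 each arm is judged separately against fixed counts (24 or more of 39 progression-free at one year), with no intended comparison between arms. Neither the bracketed volume nor the product strength enters the sample size, that decision rule, the futility boundaries or the error rates.

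**The case for a change.** The strongest case for a change rests on practice rather than on calculation. Syringes are filled by volume, so the millilitre figure is the one most likely to reach a patient's instruction sheet. The patient logbook, as Section 9.0 describes it, records when and where the injection was given, so it would not reveal a mismatch of form and volume. Other centers work under their own IND with an identical protocol and could stock a different form, while one of the fallback sources in Section 5.3 is an intranet page of the lead center. Section 3.0 also relies partly on this study's different GM-CSF dose when it answers reports of a harmful adjuvant effect, so the delivered dose is not a matter of indifference. Naming the strength would cost a few words.

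Two parts of this stand. The volume is unlabelled, and the powder text is more than a passing mention. The step from there to a defect in the plan does not stand. Section 5.3 states the mass first, gives both strengths within a few lines, and directs the reader to the package insert. Pharmacy staff preparing either form have the mass and the concentration in front of them. The self-injection and multi-center scenarios describe how an error might spread if one were made; they do not show that the plan directs one. Appendices 2, 4 and 6 may already give the form or the volume, so it cannot be said that the full plan leaves it open.

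**Conclusion.** The observation is accurate but calls for no change to the plan. No stated figure is wrong: 70 mcg in 0.14 mL is exact for the 500 mcg/mL liquid, and the mass dose is consistent wherever it appears. What is absent is a label saying which form the bracket belongs to, and a reader can recover that from the same paragraph by one division.

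The largest discrepancy the text can support is 35 mcg against 70 mcg per injection, or 70 mcg against 140 mcg per cycle. It arises only if the powder is used and its volume is taken from the bracket. That is a conditional figure, not an estimate of what happened; the documents do not say which form any site dispensed. The trial's sample size, decision rule and error rates do not depend on it.

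This conclusion assumes a nominal 250 mcg/mL for the reconstituted powder, and that those preparing doses work from the prescribed mass. Reconciling the bracketed volume with the two described strengths is clerical housekeeping for the sponsor, for instance when Section 5.3 is next opened, together with a check that the administration log agrees. Nothing here is a view on which form, volume or dose is right.
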